#### 7.3.2. Subgroup Analyses for Objective Response Rate

Subgroups will be formed based on the following participant characteristics and baseline variables for those participants whose data are available:

- Age: < 65 years,  $\ge 65$  years
- Gender: male, female
- Race: white, others
- Geographic region: Europe, North America, rest of world
- Current FL grade: 1, 2, 3a
- Current Ann Arbor Staging: I-II, III-IV
- Current FLIPI risk category: low (0 1), intermediate (2), high  $(\ge 3)$
- Number of prior systemic therapy regimens:  $< 3, \ge 3$
- Bone marrow involvement at baseline: yes, no, unknown
- ECOG performance status:  $\leq 1 \text{ vs } 2$
- Bulky disease at baseline: longest diameter  $\geq 10$  cm vs < 10 cm at baseline by IRC
- Relapsed/refractory status to the most recent prior therapy: relapsed, refractory, unknown

Subgroups may be further divided or combined based on emerging data. The ORR as determined by IRC and its 95% exact binomial CIs will be provided for participants for each subgroup. A forest plot will be created to summarize the variability in ORR as determined by the IRC for participants across subgroups.

## 7.4. Analysis of the Secondary Efficacy Parameter

#### 7.4.1. Complete Response Rate

Complete response rate is the percentage of participants with a best overall response of CR as defined by revised response criteria for lymphomas (Cheson et al 2014). For responses determined by the IRC, the best overall response for each participant will be provided by the Clinical Reviewer. Participants who do not have sufficient baseline or on-study response assessment information to be adequately assessed for response status will be included in the denominators in the calculation of CRR.

The CRR as determined by the IRC will be estimated with 95% CIs. Confidence intervals will be calculated based on the exact method for binomial distributions.

A sensitivity analysis of CRR will be provided to summarize participants who switched to the selected treatment regimen after starting the maintenance dose as a separate treatment regimen.

#### 7.4.2. **Duration of Response**

Duration of response is defined as the time from first documented evidence of CR or PR until disease progression or death due to any cause among participants who achieve an objective response (ie, CR or PR), as determined by revised response criteria for lymphomas (Cheson et al 2014). For responses assessed by the IRC, the date of initial response and date of disease progression will be provided by the Clinical Reviewer for participants who have achieved best response of CR or PR. Censoring of DOR will follow the same algorithm as the censoring of PFS (see Section 7.4.3).

The total number of responders per the IRC, the number of participants whose disease progressed per the IRC or who died, and the number of participants censored will be summarized by treatment groups and combined. The Kaplan-Meier estimate of median DOR as determined by the IRC will be presented with its 95% CI, with the CIs calculated using the generalization of Brookmeyer and Crowley's method (1982) with log-log transformation (Klein and Moeschberger 1997).

A sensitivity analysis of DOR will be performed where response assessments after the time of crossover will be excluded from the determination of DOR for participants who switched to the selected treatment regimen after starting the maintenance dose. Crossover participants who have not progressed at the time of crossover will be censored at the last valid radiologic assessment on/before the time of crossover. Participants who failed to achieve a response of CR or PR on/before the time of crossover will not be considered as responders for this analysis.

#### 7.4.3. Progression-Free Survival

Progression-free survival is defined as the time from the date of the first dose of the study drug to the first documented disease progression as determined by revised response criteria for lymphomas (Cheson et al 2014), or death due to any cause, whichever occurs first. For responses assessed by IRC, date of disease progression will be provided by the Clinical Reviewer. Censoring for PFS will follow the algorithm outlined in Table 2, which is based on FDA Guidance for Industry: Clinical Trial Endpoints for the Approval of Non-Small Cell Lung

Cancer Drugs and Biologics (2015) and Guidance for Industry: Clinical Trial Endpoints for the Approval of Cancer Drugs and Biologics (2018).

Table 2: Evaluation and Censoring of Progression-Free Survival

Situation	Outcome	Date of Progression or Censoring
No baseline tumor assessments	Censored	Day 1
No valid postbaseline response assessments	Censored	Day 1
Progression documented between scheduled response assessments	Progressed	Date of first overall response of PD
No progression	Censored	Date of last valid radiologic assessment (not NE and not missing)
Study discontinuation for undocumented progression	Censored	Date of last valid radiologic assessment (not NE and not missing)
Study discontinuation for toxicity or other reason	Censored	Date of last valid radiologic assessment (not NE and not missing)
New anticancer treatment started	Censored	Date of last valid radiologic assessment (not NE and not missing) on/before starting a new anticancer treatment
Death before first progressive response assessment	Progressed	Date of death
Death between adequate response assessments	Progressed	Date of death
Death or progression after two or more missed assessments	Censored	Date of last valid radiologic assessment (not NE and not missing) before the missed assessments

NE = not evaluable.

The number of participants whose disease progressed per the IRC or who died, and the number of participants censored will be summarized by treatment groups and combined. The Kaplan-Meier estimate of median PFS as determined by the IRC will be presented with its 95% CIs, with the CIs calculated using the generalization of Brookmeyer and Crowley's method (1982) with log-log transformation (Klein and Moeschberger 1997). Progression-free survival rates at 6, 12, 18, 24, and 36 months will also be provided with 95% CIs calculated using Greenwood's formula to estimate the standard error.

A sensitivity analysis of PFS will be performed where response assessments after the time of crossover will be excluded from the determination of PFS for participants who switched to the selected treatment regimen after starting the maintenance dose. Crossover participants who have not progressed at the time of crossover will be censored at the last valid radiologic assessment on/before the time of crossover.

#### 7.4.4. Overall Survival

Overall survival is defined as the time from the date of the first dose of study drug to death due to any cause. For participants who are still alive at the time of the analysis, OS will be censored on the date the participant is last known to be alive.

[figure not shown]
The number of participants who died and the number of participants censored will be summarized by treatment groups and combined. The Kaplan-Meier estimate of median OS will be presented with its 95% CIs, with the CIs calculated using the generalization of Brookmeyer and Crowley's method (1982) with log-log transformation (Klein and Moeschberger 1997). Survival rates at 6, 12, 18, 24, and 36 months will also be provided with 95% CIs calculated using Greenwood's formula to estimate the standard error.

#### 7.4.5. Best Percentage Change in Target Lesion Size

For participants in the FAS with measurable lesions at baseline, target lesion sizes will be measured by the sum of the product of diameters of all target lesions. The best percentage change from baseline, defined as the largest decrease in target lesion sizes during the study, will be summarized by treatment groups and combined. A waterfall plot of the best percentage change (2 treatment groups combined) will be generated using data from the IRC. Note that for participants who only have increases in target lesion sizes from baseline, the smallest increase will be considered as the best change from baseline. For the IRC, two radiologic reviewers will conduct separate reviews for each participant. An adjudication will be performed per the Independent Review Charter when Reviewers 1 and 2 disagree on the CT/MRI best overall response, or when best overall response is consistent, but the date of initial response and/or the date of progression differ between Reviewers 1 and 2. The adjudicator will select the read that he or she believes more accurately reflects the adjudication parameter(s) in question. This is considered the "accepted read," and data from this reviewer will be used for the analysis. When there is no adjudication needed, data from Reviewer 1 will be used for the analysis. An indicator will be provided to identify the read that is considered to be the accepted assessment in data from the IRC.

Best change in target lesion size as reported by the investigator will also be summarized as described above. Target lesions considered "too small to measure" will be assigned a default value of 5 mm × 5 mm for purposes of this analysis. Likewise, target lesions identified as "not present" at postbaseline assessments will be assigned 0 mm × 0 mm for this analysis. In the event that a target lesion is unaccounted for in a particular postbaseline timepoint (ie, the assessment is missing or NE), then the overall sum of target lesions will not be evaluable for that postbaseline timepoint.

#### 9. SAFETY AND TOLERABILITY

Appendix A provides a list of planned tables, figures, and listings. Sample data displays are included in a separate document.

#### 9.1. General Considerations

Summary tables may be replaced with listings when appropriate. For instance, an AE frequency table may be replaced with a listing if it only contains a few unique preferred terms reported on relatively few participants.

#### 9.2. Adverse Events

#### 9.2.1. Adverse Event Definitions

A TEAE is any AE either reported for the first time or worsening of a pre-existing event after the first dose of study drug and within 30 days of the last administration of study drug regardless of starting new anti-lymphoma therapy. Analysis of AEs (as discussed below) will be limited to TEAEs, but data listings will include all AEs regardless of their timing in relation to study drug administration. For purposes of analysis, all AEs will be considered TEAEs unless the AE can unequivocally be defined as not treatment-emergent.

Adverse events will be tabulated by MedDRA PT and SOC. Severity of AEs will be graded using the NCI CTCAE (v4.03; NCI 2010), Grades 1 through 5. The CTCAE reporting guidelines and grading details are available on the Cancer Therapy Evaluation Program website.

The subset of AEs considered by the investigator to be related to study drug will be considered treatment-related AEs. If the investigator does not specify the relationship of the AE to study drug, the AE will be considered treatment-related. The incidence of AEs and treatment-related AEs will be tabulated. In addition, serious TEAEs will also be tabulated.

#### 9.2.2. Adverse Events of Special Interest

The number of participants who experienced TEAEs of special interest listed below will be summarized by maximum severity.

- Colitis
- Diarrhea
- Exfoliative dermatitis
- Febrile neutropenia
- Rash
- Intestinal perforation
- Pneumonitis
- Pneumonia
- PJP infection
- CMV infection
- Herpes simplex
- Varicella zoster virus infection

The time to onset of a TEAE is defined as the interval between the date of first dose of study drug and the date of the first occurrence of a TEAE. Participants who have not experienced a TEAE at the time of analysis will be right-censored at the earlier of 30 days after the last dose date and date of last study visit through the end of safety follow-up. If participants have missing or partial last dose dates of study drug or onset date of a TEAE, the partial or missing dates will be handled using the rules explained in Section 4.1.4.

Summaries of time to onset of new or worsening Grade 3 or higher AEs will be provided using descriptive statistics and the life-table method for rash, colitis, diarrhea, febrile neutropenia, pneumonia, herpes simplex, and varicella zoster virus infection. In addition, summaries of time to onset of new or worsening AEs of any grade will be provided using descriptive statistics and the life-table method for colitis, diarrhea, exfoliative dermatitis, intestinal perforation, pneumonia, pneumonitis, PJP infection, CMV infection, herpes simplex, and varicella zoster virus infection. Kaplan-Meier plots of time to onset of new or worsening Grade 3 or higher AEs will be provided for rash, colitis, and diarrhea. In addition, Kaplan-Meier plots of time to onset of new or worsening AEs of any grade will be provided for colitis and diarrhea.

Descriptive statistics of time to onset of these TEAEs of special interest are based on all participants who have experienced a TEAE at the time of analysis. To summarize these TEAEs of special interest using the life-table method, the effective sample size is defined as the number of participants at the beginning of interval minus half the participants censored in the interval. The conditional proportion is calculated as the number of first events divided by the effective sample size in the interval.

The longest duration of a TEAE of any grade is defined as the longest interval between the date of occurrence of a TEAE and the date of resolution. The longest duration of a Grade 3 or higher TEAE is defined as the longest interval between the date of occurrence of a Grade 3 or higher TEAE and the date of improvement to Grade 2 or lower. If participants have missing or partial onset/end date of a TEAE, the partial or missing dates will be handled using the rules explained in Section 4.1.4. Participants who have missing end date of a TEAE at the time of analysis will be right-censored using the following algorithm:

- If the TEAE is serious, then the participant will be censored at the earlier date of data cutoff, study discontinuation, and death.
- If the TEAE is not serious,
  - If the participant is ongoing with study treatment, then the participant will be censored at the data cutoff date, OR
  - If the participant discontinued treatment, then the participant will be censored at date of safety follow-up visit, or 35 days after the end of treatment visit (or after the last dose if the end of treatment visit was not performed), whichever is later; the censored date will be truncated by the earlier date of data cutoff, study discontinuation, and death if beyond.

Longest duration of new or worsening Grade 3 or higher colitis, diarrhea, rash, and febrile neutropenia will be summarized. In addition, longest duration of new or worsening AEs of any grade will be summarized for colitis, diarrhea, and rash.

The total number of participants whose TEAE of any grade resolved or whose Grade 3 or higher TEAE improved to Grade 2 or lower and the number of participants censored will be summarized. The Kaplan-Meier estimate of median time to resolution/improvement and its 95% CIs will be provided, with the CIs calculated using the generalization of Brookmeyer and Crowley's method (1982) with log-log transformation (Klein and Moeschberger 1997). Resolution/improvement rates at selected timepoints will also be provided with 95% CIs calculated using Greenwood's formula to estimate the standard error.

TEAEs of special interest to be summarized may be adjusted based on emerging data.

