INCB050465 is being evaluated as a monotherapy in a Phase 1/2, dose-escalation and expansion study (INCB 50465-101, NCT02018861, [Phillips et al 2016](#)). As of 01 MAR 2017, data were available for 63 subjects who received INCB050465 administered orally QD or QD for 9 weeks followed by QW. Starting in NOV 2016, subjects were switched to QW dosing if they had been on study treatment for > 9 weeks ([Ramchandren et al 2017](#)). The median duration of treatment for all subjects was 114 days (range 7-520). Nonhematological adverse events observed in \geq 20% of subjects were nausea (38%), diarrhea/colitis (35%), fatigue (29%), vomiting (27%), cough (24%), rash (22%), and dizziness (21%). New or worsening Grade \geq 3 anemia, thrombocytopenia, and neutropenia occurred in 5%, 10%, and 22% of subjects, respectively. No \geq Grade 3 nonhematological treatment-related AEs were reported in \geq 10% of subjects. Serious AEs that occurred in \geq 2 subjects included diarrhea/colitis (n = 6) and hypotension (n = 3) and ventricular tachycardia, pyrexia, pneumonia, exfoliative dermatitis, syncope, and bacteremia (n = 2 each). Twelve (19%) of the 63 subjects discontinued study treatment due to the following AEs: diarrhea (n = 2), exfoliative dermatitis (n = 2), colitis, cytomegalovirus colitis, pneumonitis, rash, psoriasis, neutropenia, pneumonia, and hypercalcemia (n = 1 each). All but 1 of these events occurred after the 9-week disease assessment. No liver function test abnormalities > Grade 1 were reported while subjects were receiving study treatment. No dose-limiting toxicities were identified, and the maximum tolerated dose was not reached.

As of 01 MAR 2017, 28 objective responses as reported by investigators were observed in 57 evaluable subjects with DLBCL, FL, HL, marginal zone lymphoma, chronic lymphocytic leukemia, and mantle cell lymphoma. These results include 8 objective responses among the 11 evaluable subjects with FL; all but 1 of the objective responses occurred by the time of the 9-week disease assessment. Among the 8 objective responses, 6 demonstrated > 75% reduction in their target lesions (see [Figure 1](#)). The longest duration of study treatment among subjects with FL was approximately 14 months, with 3 of the evaluable subjects ongoing.

Figure 1: Best Percentage Change From Baseline in Target Lesion Size in Follicular Lymphoma Subjects From Study INCB 50465-101

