
 Diarrhea (≥ Grade 3). Noninfectious colitis (any grade; confirmed or suspected). 	
Step 1: Interrupt INCB050465. Perform work-up for infection (including CMV, C. difficile, etc) immediately. Initiate or continue supportive care (see Section 5.4.1.2). Consider colonoscopy with biopsy for diarrhea ≥ Grade 3 and/or if symptoms^a suggestive of colitis. Monitor every 48 hours until resolution.
 
Step 2: If infection* is ruled out, start oral steroids, or consider IV steroids if participant is being given IV fluids. If no improvement with oral steroids within 48 hours, switch to IV steroids.
 
*For infectious diarrhea/colitis, follow institutional standard of care guidelines and restart pascalisib according to clinical judgement after resolved to ≤ Grade 1. Consult with medical monitor if needed.
 
Step 3: When diarrhea/colitis resolves to ≤ Grade 1, continue supportive care and taper steroids according to institutional standard of care. When taper is complete (eg, no steroid or ≤ 10 mg/day prednisone or equivalent) and diarrhea/colitis is ≤ Grade 1, restart INCB050465 as described herein and with approval of the medical monitor. Continue to monitor.
 
  
 INCB050465 Current Dose	Dose Modification	
   
 Any dose with QD dosing	20 mg QW regardless of Treatment A or B assignment	
 
 20 or 10 mg QW	Restart next lower dose	
 
 5 mg QW	Permanently discontinue	
  
 
Step 4: If ≥ Grade 3 diarrhea/colitis (any grade) reoccurs, permanently discontinue INCB050465.
	INCB050465 Current Dose	Dose Modification	Any dose with QD dosing	20 mg QW regardless of Treatment A or B assignment	20 or 10 mg QW	Restart next lower dose	5 mg QW	Permanently discontinue
INCB050465 Current Dose	Dose Modification								
Any dose with QD dosing	20 mg QW regardless of Treatment A or B assignment								
20 or 10 mg QW	Restart next lower dose								
5 mg QW	Permanently discontinue								

^a Diarrhea accompanied by abdominal pain and/or mucus or blood in stool.

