8.1.2. Reporting

Adverse events that begin or worsen after informed consent should be recorded on the Adverse Events form of the eCRF. Conditions that were already present at the time of informed consent should be recorded on the Medical History form in the eCRF. Monitoring for the occurrence of new AEs should be continued for at least 30 days after the last dose of study drugs. Adverse events (including laboratory abnormalities that constitute AEs) should be described using a diagnosis whenever possible rather than by individual underlying signs and symptoms. When a clear diagnosis cannot be identified, each sign or symptom should be reported as a separate AE.

The term "disease progression" should be recorded as an AE/SAE only if there are no other identifiable AEs/SAEs associated with the disease progression at the time of reporting. For events associated with disease progression, the relevant signs and symptoms should be reported using a diagnosis whenever possible rather than individual underlying signs and symptoms. When a clear diagnosis cannot be identified, each sign or symptom should be reported as a separate AE. If the events resulting from disease progression meet the criteria for an SAE (eg, resulted in hospitalization, a life-threatening event, or death), the specific event(s) should be reported as an SAE(s) as described in Section 8.3.2. In both cases (ie, AEs or SAEs related to disease progression), it should be indicated that each event (reported as a diagnosis or as signs and symptoms) is related to disease progression on the Adverse Events form of the eCRF.

The severity of AEs will be assessed using CTCAE v4.03 (NCI 2009) Grades 1 through 5. If an event is not classified by CTCAE, the severity of the AE will be graded according to the scale below to estimate the grade of severity:

Grade 1	Mild; asymptomatic or mild symptoms; clinical or diagnostic observations only; intervention not indicated.
Grade 2	Moderate; minimal, local, or noninvasive intervention indicated; limiting age-appropriate activities of daily living.
Grade 3	Severe or medically significant but not immediately life-threatening; hospitalization or prolongation of hospitalization indicated; disabling; limiting self-care activities of daily living.
Grade 4	Life-threatening consequences; urgent intervention indicated.
Grade 5	Death due to AE

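### No planned table or curve gives diarrhea and colitis combined, although the protocol pools them in its earlier data and manages their more severe forms together

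*SAP*

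**What the plan says.** SAP Section 9.2.2 has separate entries for colitis and diarrhea in its list of adverse events of special interest. Each is summarised on its own by maximum severity, by time to onset (descriptive statistics, life table and Kaplan-Meier) and by longest duration, at any grade and at Grade 3 or higher. On the severe-event curves it says "Kaplan-Meier plots of time to onset of new or worsening Grade 3 or higher AEs will be provided for rash, colitis, and diarrhea". The general adverse event tables in SAP Section 9.2.3 are by system organ class and preferred term. No table, figure or listing title in SAP Appendix A names a combined event.

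The protocol uses both approaches.

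- **Pooled.** Section 1.3 reports the earlier monotherapy study, where "data were available for 63 subjects who received INCB050465", with diarrhea/colitis as one adverse event at 35% and as the most frequent serious event listed (n = 6). Table 5 in Section 5.4.1.2 covers both conditions. One of its rows holds diarrhea of Grade 3 or higher together with "Noninfectious colitis (any grade; confirmed or suspected"), under shared steps and a shared recurrence rule.
- **Separate.** Section 8.5 lists colitis and diarrhea of Grade 2 or higher as two events of special interest. Table 5 gives Grade 1 and Grade 2 diarrhea their own rows. Section 1.3 lists treatment discontinuations by individual term.

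On recording, Protocol Section 8.1.2 says adverse events "should be described using a diagnosis whenever possible rather than by individual underlying signs and symptoms", and that signs or symptoms are reported where no clear diagnosis can be made. Table 5 asks sites only to consider colonoscopy with biopsy.

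**The concern.** If one toxicity can be recorded under either of two terms, a summary of each term alone may miss part of it. A site that investigates and reaches a diagnosis may record colitis, while a site that does not may record diarrhea. Each separate rate would then reflect recording practice as well as the drug.

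The curves have the same weakness. Suppose diarrhea is recorded at no more than Grade 2 and the illness is then recorded as Grade 3 colitis. That participant has no event on the Grade 3 or higher diarrhea curve. If treatment stops for the colitis, the participant is censored on the diarrhea curve no later than 30 days after the last dose. That censoring follows from a closely related event, so it may be informative. An episode that changes term is also split into two shorter durations.

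At stake is a plain safety question: how many participants had diarrhea or colitis, how soon, and for how long. The planned summaries do not answer it.

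**Working it through.** **1. Reproduce the document's pooled figure.** Protocol Section 1.3 gives 35% of 63 subjects. The only whole number that rounds to 35% is 22: 22/63 = 34.9%, whereas 21/63 = 33.3% and 23/63 = 36.5%. The exact 95% CI for 22/63 is 23.3% to 48.0%. Pooled serious events are 6/63 = 9.5%. The figure is consistent and counts the two terms together.

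**2. What two separate rows can say about the combined count.** Let d and c be the numbers of participants with a diarrhea term and a colitis term, out of N. The number with either lies between max(d, c), when one group is nested in the other, and min(N, d + c), when no participant has both. The inputs below are assumptions; only N = 120 (SAP Section 3.3) comes from the documents.

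| Assumed diarrhea | Assumed colitis | Combined, lower | Combined, upper |
|---|---|---|---|
| 36 (30%) | 12 (10%) | 36 (30%) | 48 (40%) |
| 42 (35%) | 18 (15%) | 42 (35%) | 60 (50%) |
| 12 (10.0%), Grade 3 or higher | 8 (6.7%), Grade 3 or higher | 12 (10.0%) | 20 (16.7%) |

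The width of each range is the smaller of the two rates. A reader of the tables cannot tell whether to add the rows or take the larger one.

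**3. Effect of recording practice when the toxicity does not change.** Assume 42 of 120 participants (35.0%) are affected and each has exactly one term.

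| Recorded as colitis | Diarrhea row | Colitis row | Either |
|---|---|---|---|
| 0 of 42 | 42 (35.0%) | 0 (0%) | 42 (35.0%) |
| 4 of 42 | 38 (31.7%) | 4 (3.3%) | 42 (35.0%) |
| 10 of 42 | 32 (26.7%) | 10 (8.3%) | 42 (35.0%) |
| 21 of 42 | 21 (17.5%) | 21 (17.5%) | 42 (35.0%) |

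The diarrhea row moves from 35.0% to 17.5% through labelling alone. A composite row would stay at 35.0% (exact 95% CI 26.5% to 44.2%).

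**4. Does another planned output supply the number?** The gastrointestinal system organ class row is no substitute, because it would also count events such as nausea and vomiting (38% and 27% in the earlier study). Listing 2.7.1 holds all adverse events, so a combined count could be made by hand afterwards. It would then have no prespecified term list or counting rule.

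**The case against.** The case for leaving the SAP as it is has substance.

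- **The SAP follows the protocol.** Protocol Section 8.5 lists the two events separately, and Section 9.4.2.5 leaves their summary to the SAP. This stands: there is no conflict between the documents, only an analysis choice.
- **Joint management is partial.** Grade 1 and Grade 2 diarrhea have their own steps in Table 5, and the earlier discontinuations are listed as diarrhea (2), colitis (1) and cytomegalovirus colitis (1) among 12. This stands. The pooling is clear for the earlier adverse event and serious event frequencies, and for the shared Table 5 row.
- **The recording effect is inferred.** Section 8.1.2 does not require endoscopy for a diagnosis, and Table 5 recognises suspected colitis, so a site could record colitis without a scope. The text allows the effect but does not show that it happens.
- **The example of a missed severe event is conditional.** Section 8.1.2 records each change of severity as a separate event. Diarrhea that reaches Grade 3 before colitis is recorded would count on both severe-event curves. In the other case the participant still counts on both any-grade curves.
- **The plan is flexible.** SAP Section 9.2.2 lets the list of events be adjusted, the preferred terms behind each label are not given, and the table shells are in a separate document. A combined term could still be added, but none is specified in the text available.

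Four stronger readings are tempting, and the documents do not support them.

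1. A reader might infer that no planned output gives the rate of the drug's main toxicity. Separate rates are planned, and no document uses that label. Nausea was more frequent in the earlier study (38%), and Grade 3 or higher neutropenia occurred in 22%.
2. A reader might infer that the result has to be compared with the earlier 35%. Protocol Section 4.2 excludes comparison with historical controls, and the 63 subjects received other schedules.
3. A reader might expect a composite to show how often Table 5 is triggered. The first of either term would mix grades and causes that Table 5 handles differently. Planned Tables 3.2.18 to 3.2.20, on events leading to reduction, interruption and discontinuation, are closer to that question.
4. A reader might infer that each separate rate must understate the combined one. If every participant with colitis also has a diarrhea term, the diarrhea rate equals the combined rate.

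**Conclusion.** The point holds as a minor, free improvement. The SAP plans incidence, onset and duration for diarrhea and for colitis, consistent with Protocol Section 8.5. No visible planned output gives the rate, the time to first event or the duration of the two combined. Because the recorded term may depend on discretionary work-up, each separate rate can understate the combined toxicity, and the planned rows only bound it.

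The size depends on rates that the documents do not give. The uncertainty equals the smaller of the two rates: 10 percentage points (12 of 120 participants) at an assumed 30% and 10%, and 15 points at an assumed 35% and 15%. The recording-practice table further assumes one term per participant. The direction of any bias from censoring is not established; it is a reason to show time to the first of either event. The sample size, the primary analysis and the separate safety summaries are unaffected.

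**What to change.** In SAP Section 9.2.2, add one composite event of special interest, diarrhea/colitis, and keep the two separate terms as its components. Specify:

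- the preferred terms that belong to it, including whether infectious forms such as cytomegalovirus colitis count;
- one count per participant, with onset at the first of either term and severity at the highest grade of either;
- duration until both have resolved or, for Grade 3 or higher, until both have improved to Grade 2 or lower, in line with the SAP's existing definition;
- results for any grade and for Grade 3 or higher.

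Report it in Tables 3.2.26 to 3.2.29 and Figures 4.5.1 and 4.5.2. The cost is one grouped term in the adverse event dataset and one extra row or curve per output. It needs no new data and no change to sample size or clinical management.
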